8.4.2 Method of Detecting AEs, SAEs, and Other Reportable Safety Events

Care will be taken not to introduce bias when detecting AEs and/or SAEs and other reportable safety events. Open-ended and nonleading verbal questioning of the participant is the preferred method to inquire about AE occurrence.

8.4.3 Follow-up of AE, SAE, and Other Reportable Safety Event Information

After the initial AE/SAE report, the investigator is required to proactively follow each participant at subsequent visits/contacts. SAEs and other reportable safety events, including pregnancy and exposure during breastfeeding, ECIs, cancer, and overdose will be followed until resolution, stabilization, until the event is otherwise explained, or the participant is lost to follow-up (as defined in Section 7.3). The investigator will also make every attempt to follow nonserious AEs that occur in randomized participants for outcome. Further information on follow-up procedures is given in Appendix 3.

8.4.4 Regulatory Reporting Requirements for SAE

08X3SB

Prompt notification (within 24 hours) by the investigator to the Sponsor of SAE is essential so that legal obligations and ethical responsibilities toward the safety of participants and the safety of a study intervention under clinical investigation are met.

The Sponsor has a legal responsibility to notify both the local regulatory authority and other regulatory agencies about the safety of a study intervention under clinical investigation. The Sponsor will comply with country-specific regulatory requirements and global laws and regulations relating to safety reporting to regulatory authorities, IRB/IECs, and investigators.

Investigator safety reports must be prepared for SUSARs according to local regulatory requirements and Sponsor policy and forwarded to investigators as necessary.

An investigator who receives an investigator safety report describing an SAE or other specific safety information (eg, summary or listing of SAEs) from the Sponsor will file it along with the IB and will notify the IRB/IEC, if appropriate according to local requirements.

8.4.5 Pregnancy and Exposure During Breastfeeding

Although pregnancy and infant exposure during breastfeeding are not considered AEs, any pregnancy or infant exposure during breastfeeding (spontaneously reported to the investigator or their designee) that occurs in a participant during the study are reportable to the Sponsor.

All reported pregnancies must be followed to the completion/termination of the pregnancy. Any pregnancy complication will be reported as an AE or SAE.

The medical reason (example: maternal health or fetal disease) for an elective termination of a pregnancy will be reported as an AE or SAE. Prenatal testing showing fetus will be born with severe abnormalities/congenital anomalies that leads to an elective termination of a pregnancy will be reported as an SAE for the fetus.

Pregnancy outcomes of ectopic pregnancy, spontaneous abortion, missed abortion, benign hydatidiform mole, blighted ovum, fetal death, intrauterine death, miscarriage, and stillbirth must be reported as serious events (Important Medical Events). If the pregnancy continues to term, the outcome (health of infant) must also be reported.

8.4.6 Disease-related Events and/or Disease-related Outcomes Not Qualifying as AEs or SAEs

A cholinergic-related AE term has been defined and is composed of the following individual component AEs: nausea, vomiting, diarrhea, and abdominal pain.

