2.2.4 Information on Other Study-related Therapy: Donepezil Hydrocholoride

Donepezil HCl is an AChEI that is indicated for symptomatic treatment of mild-to-moderate AD. Standard dosing is donepezil HCl 10 mg, 1 tablet PO daily. The most common AE of donepezil HCl, defined as those occurring at a frequency of at least 5% in patients receiving 10 mg/day and twice the placebo rate, are largely predicted by the cholinomimetic effects of donepezil HCl, including nausea, diarrhea, insomnia, vomiting, muscle cramps, fatigue and anorexia. These AEs are typically of mild intensity and transient, resolving during continued donepezil HCl treatment without the need for dose modification [Jack, C. R. Jr., et al 2018]. Less commonly observed AEs include depression and sleep disturbances (eg, abnormal

dreams and somnolence). Donepezil HCl is \sim 96% bound to human plasma proteins, mainly to albumins (\sim 75%) and alpha-1 acid glycoprotein (about 21%) over the concentration range of 2 to 1000 ng/mL. Donepezil HCl is both excreted in the urine intact and extensively metabolized to 4 major metabolites, 2 of which are known to be active, and a number of minor metabolites, not all of which have been identified. Donepezil HCl is metabolized by CYP 450 isoenzymes 2D6 and 3A4 and undergoes glucuronidation. Donepezil HCl has a Tmax of \sim 3 to 4 hours and $t1/2 \sim$ 70 hours.

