4.2.1 Rationale for Endpoints

4.2.1.1 Safety Endpoints

08X3SB

A cholinergic-related AE term has been defined and is composed of the following individual component AEs: nausea, vomiting, diarrhea, and abdominal pain.

Prospective assessment of suicidal ideation and behavior will be performed in this study using the C-SSRS.

Based on data from the preclinical toxicology and safety studies as well as clinical safety data from PN001, PN002, PN004, PN006 and PN007 Panel A (Section 2.2.3), it is expected that multiple-day administration of MK-1167 up to 6 mg daily for 31 days will be well tolerated in study participants with AD maintained on a stable dose of donepezil 10 mg daily.

No specific target organ toxicities have been identified in preclinical studies conducted with MK-1167 to date. In PN001 and PN002, single-dose administration of MK-1167 up to 76 mg and multiple-dose administration up to 8 mg daily was generally well tolerated in healthy younger adult study participants. In PN004, multiple-day oral loading doses of MK-1167 10 mg/PBO for 3 days following by maintenance doses of oral doses of MK-1167/PBO 3 mg daily for 13 days were generally well tolerated in healthy elderly study participants (Section 2.2.2). In PN007 Panel A, multiple-day oral loading doses of MK-1167/PBO 6 mg for 7 days following by maintenance doses of oral doses of MK-1167/PBO 3 mg daily for 14 days were generally well-tolerated in participants with AD maintained on a stable baseline dose of donepezil 10 mg (Section 2.2.3).

CCI

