10.3.2 Definition of AE

AE definition

08X3SB

An AE is any untoward medical occurrence in a clinical study participant, temporally associated with the use of study intervention, whether or not considered related to the study intervention.

Note: An AE can therefore be any unfavorable and unintended sign (including an abnormal laboratory finding), symptom, or disease (new or exacerbated) temporally associated with the use of a study intervention.

Note: For purposes of AE definition, study intervention includes any pharmaceutical product, biological product, vaccine, diagnostic agent, medical device, combination product, or protocol-specified procedure whether investigational or marketed (including placebo, active comparator product, or run-in intervention), manufactured by, licensed by, provided by, or distributed by the Sponsor for human use in this study.

Events meeting the AE definition

Any abnormal laboratory test results (hematology, clinical chemistry, or urinalysis) or other safety assessments (eg, ECG, radiological scans, vital signs measurements), including those that worsen from baseline, considered clinically significant in the medical and scientific judgment of the investigator.

Exacerbation of a chronic or intermittent preexisting condition including either an increase in frequency and/or intensity of the condition.

New conditions detected or diagnosed after study intervention administration even though it may have been present before the start of the study.

Signs, symptoms, or the clinical sequelae of a suspected drug-drug interaction.

Signs, symptoms, or the clinical sequelae of a suspected overdose of either study intervention or a concomitant medication.

For all reports of overdose (whether accidental or intentional) with an associated AE, the AE term should reflect the clinical symptoms or abnormal test result. An overdose without any associated clinical symptoms or abnormal laboratory results is reported using the terminology "accidental or intentional overdose without adverse effect."

Any new cancer or progression of existing cancer.

Events NOT meeting the AE definition

Medical or surgical procedure (eg, endoscopy, appendectomy): the condition that leads to the procedure is the AE.

Situations in which an untoward medical occurrence did not occur (social and/or convenience admission to a hospital).

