Anticipated day-to-day fluctuations of preexisting disease(s) or condition(s) present or detected at the start of the study that do not worsen.

Surgical procedure(s) planned prior to informed consent to treat a preexisting condition that has not worsened.

Refer to Section 8.4.6 for protocol-specific exceptions.

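### Does Section 8.4.6 take nausea, vomiting, diarrhea and abdominal pain out of adverse event reporting?

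*Combined protocol and SAP*

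**What the plan says.** Section 8.4.6 carries the heading "Disease-related Events and/or Disease-related Outcomes Not Qualifying as AEs or SAEs". One sentence is visible below it: "A cholinergic-related AE term has been defined and is composed of the following individual component AEs: nausea, vomiting, diarrhea, and abdominal pain". It names no disease-related event and states no exception.

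Section 10.3.2 (Appendix 3) has a list headed "Events NOT meeting the AE definition". The list ends with the instruction "Refer to Section 8.4.6 for protocol-specific exceptions".

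The composite is also defined in Section 4.2.1.1, Safety Endpoints, with the same opening: "A cholinergic-related AE term has been defined and is composed of the following individual component AEs", followed by the same four symptoms.

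Four other places bear on how these symptoms are handled:

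- Section 8.4.1 and Table 6 require the investigator to report all AEs from randomization through the follow-up period, which ends 14 days after cessation of intervention.
- Section 9.3.1 makes AEs of every type, and discontinuations due to them, part of the primary safety endpoint.
- Section 6.6.1 halts dosing if two or more participants in a panel at the same dose level have severe nonserious AEs, unless these are clearly unrelated to study intervention.
- Section 2.2.4 describes the common AEs of donepezil as "largely predicted by the cholinomimetic effects of donepezil HCl, including nausea, diarrhea, insomnia, vomiting", among others.

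**The concern.** The heading announces events that are not AEs, and the text beneath it speaks of AEs. Taken alone this would be a curiosity, but Section 10.3.2 makes 8.4.6 operative by sending sites there for exceptions to the AE definition. A coordinator who follows the pointer finds four named symptoms under a heading that says they do not qualify. The literal-minded conclusion would be that they need not be recorded.

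Much would rest on that conclusion if it were right. The primary endpoint is AEs and discontinuation due to AEs, one of the two stopping rules counts severe nonserious AEs, and the panels are small (12 active and 4 placebo in Panel A, 9 and 3 in Panel B). Gastrointestinal tolerability is also a live question for this drug class: Section 2.2.1 reports that a related receptor agonist was abandoned in Phase 3 because of such effects. Leaving out exactly these symptoms in patients who also take a cholinesterase inhibitor would weaken the study where it most needs to be informative.

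**Working it through.** No figure is at issue. The check is whether any two visible instructions tell a site to do different things with these four symptoms.

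**1. Does 8.4.6 exempt anything?** No. Its sentence defines a group term and labels each member an AE. To read it as an exemption, a site must let the heading override the sentence beneath it.

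**2. Does the list in 10.3.2 exempt anything relevant?** The items visible there are procedures, social or convenience admissions, day-to-day fluctuations of a pre-existing condition that does not worsen, and surgery already planned. None names the four symptoms. Gastrointestinal upset that was already present on donepezil and does not worsen could fall under the fluctuation item, but that is the usual rule and does not depend on 8.4.6.

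**3. Do the four symptoms meet the general AE definition?** Yes. Section 10.3.2 covers any untoward medical occurrence that is temporally associated with study intervention, whatever its cause. New or worsened nausea, vomiting, diarrhea or abdominal pain after dosing fits. If an interaction with donepezil is suspected, the list of qualifying events says so directly: "Signs, symptoms, or the clinical sequelae of a suspected drug-drug interaction". That item covers suspected interactions only, so it supports the reading without carrying it.

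**4. Is the general reporting rule qualified elsewhere?** No. Section 8.4.1 and Table 6 require all AEs after randomization, with no exception for these terms. Section 9.3.1 takes in AEs of every type.

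**5. How does the rest of the document describe the symptoms?** As drug effects.

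- Section 2.2.4 introduces its list with "The most common AE of donepezil HCl, defined as those occurring at a frequency of at least 5% in patients receiving 10 mg/day". That list contains 3 of the 4 component terms (nausea, diarrhea, vomiting); abdominal pain is not named.
- Section 2.2.2 counts diarrhea, vomiting and gastrointestinal pain as AEs in the single-dose study MK-1167-001, and abdominal discomfort in the multiple-dose study MK-1167-002.
- Section 4.2.1.1 files the composite under safety endpoints.

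**6. Result.** Every visible instruction gives the same answer: record and report. The disagreement is between one heading and one sentence, and no two rules conflict.

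**7. Is the visible text of 8.4.6 complete?** This cannot be settled from the public copy. Section 8.3.8.1 says that AEs of suicidal ideation or behavior are to be recorded as events of clinical interest and refers to Section 8.4.7. The visible 8.4.7, immediately after 8.4.6, lists only overdose and potential drug-induced liver injury, and carries no redaction mark. Sections 8.10.4 and 9.8 likewise show a heading with no text. Either text has been removed without a mark or there was a drafting omission. The sentence in 8.4.6 may therefore be the opening of a longer paragraph.

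**The case for a change.** The best case for acting is that the definition of an AE should leave no room for doubt when AEs are the primary endpoint, and that clearing the doubt costs almost nothing. The cross-reference from 10.3.2 fails in the visible text whichever way 8.4.6 is read, because it promises exceptions and none appears. The definition already stands in 4.2.1.1, so its copy in 8.4.6 looks misplaced, and one sentence could say whether any exception exists.

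The textual part of this stands: the heading does not fit the sentence, and the pointer leads to no visible exception. Two parts do not stand.

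The first is the harm. A site would have to take a sentence that calls symptoms AEs as saying that they are not, against the general definition and the all-AE reporting rule. The documents offer no basis for supposing that this would happen, or how often. Because MK-1167 and placebo are given double-blind (Section 6.3.3), they also offer no basis for expecting such a slip to differ by arm. It could still lower the counts overall, but that is a possibility without evidence behind it.

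The second is the firm claim that the sentence is in the wrong place. That is a reasonable inference from the duplicate in 4.2.1.1, but it assumes that the visible 8.4.6 is the whole section. If the full text goes on to say how these symptoms are handled, the sentence belongs there as a lead-in.

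**Conclusion.** This is a clerical mismatch in the visible text, and no change to the plan follows. The four symptoms are called AEs in both places that define the composite. They meet the general AE definition, come under an unqualified reporting rule, and fall within a primary endpoint that takes in all types of AEs. A site that follows the text records them, and the analyst counts them.

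The effect on AE incidence, on the primary endpoint and on the stopping rules is nil if the protocol is followed as written. The effect of a misreading cannot be sized from the documents. Rewording 8.4.6 would make the section tidier without altering what is collected, who is analysed or any result.

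The conclusion rests on two assumptions. Sites give the sentence and the reporting rule in 8.4.1 more weight than a section heading. And no text removed from 8.4.6 exempts these symptoms. If such text exists, the heading and the cross-reference would have the content they now seem to lack, and the plan would have to be judged on that text, which the public copy does not show.

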8.4.7 Events of Clinical Interest

08X3SB

Selected serious and nonserious AEs are also known as ECIs and must be reported to the Sponsor.

Events of clinical interest for this study include:

- An overdose of Sponsor's product, as defined in Section 8.5.
- Potential DILI events defined as an elevated AST or ALT laboratory value that is greater than or equal to 3× the ULN and an elevated total bilirubin laboratory value that is greater than or equal to 2× the ULN and, at the same time, an alkaline phosphatase laboratory value that is less than 2× the ULN, as determined by way of protocol-specified laboratory testing or unscheduled laboratory testing.*

*Note: These criteria are based on available regulatory guidance documents. The purpose of the criteria is to specify a threshold of abnormal hepatic tests that may require an additional evaluation for an underlying etiology. The study-site guidance for assessment and follow-up of these criteria can be found in the Investigator Study File Binder (or equivalent). It may also be appropriate to conduct additional evaluation for an underlying etiology in the setting of abnormalities of liver blood tests including AST, ALT, bilirubin, and alkaline phosphatase that do not meet the criteria noted above. In these cases, the decision to proceed with additional evaluation will be made through consultation between the study investigators and the Sponsor Clinical Director. However, abnormalities of liver blood tests that do not meet the criteria noted above are not ECIs for this study.

8.5 Treatment of Overdose

For purposes of this study, an overdose will be defined as any dose of any study intervention administered that exceeds the dose prescribed by the protocol. It is up to the investigator or the reporting physician to decide whether a non-study intervention dose (eg, rescue or concomitant medication) is to be considered an overdose, in consultation with the Sponsor.

Sponsor does not recommend specific treatment for any overdose. Decisions regarding dose interruptions or modifications will be made by the investigator in consultation with the Sponsor Clinical Director based on the clinical evaluation of the participant.

8.6 Pharmacokinetics

The decision as to which plasma and/or urine samples collected will be measured for evaluation of PK/pharmacodynamics will be collaboratively determined by the Sponsor (eg, samples at lower doses may not be measured if samples at higher doses reveal undetectable drug concentrations). If indicated, these samples may also be measured and/or pooled for assay in an exploratory manner for metabolites and/or additional pharmacodynamic markers.

8.6.1 Blood Collection for Plasma MK-1167

Sample collection, storage, and shipment instructions for plasma samples will be provided in the Operations Manual.

8.7 Pharmacodynamics

[figure not shown]
Tools for cognitive assessment, such as the DSST (processing speed and working memory), may be useful to assess effects on cognition. The DSST is a rapid assessment of cognitive function that will be included in the current study

8.8 Biomarkers

- Blood for Genetic Analysis
- CCI

8.8.1 Planned Genetic Analysis Sample Collection

The planned genetic analysis sample should be obtained pre-dose on Day 1 but may be collected at the next scheduled visit, if needed. Sample collection, storage, and shipment instructions for planned genetic analysis samples will be in the operations/laboratory manual.

8.9 Future Biomedical Research Sample Collection

All sample collections for study-specific assessments shown in the SoA are described within the main Informed Consent.

If the participant has provided documented informed consent for FBR, leftover samples will be used for FBR. The following specimens will be included for FBR:

Leftover samples listed in Section 8.8.

8.10 Visit Requirements

Visit requirements are outlined in Section 1.3. Specific procedure-related details are provided in Section 8.

8.10.1 Screening

08X3SB

Within approximately 4 weeks; before intervention randomization, potential participants will be evaluated to determine that they fulfill the entry requirements as set forth in Section 5.

Rescreening is defined as a separate screening period and be initiated as needed, by the investigator after consultation with the Sponsor, including for screen failures (Section 5.4).

Participants may be rescreened after consultation with the Sponsor. Rescreening is to include all screening procedures listed in the SoA (Section 1.3), including consent review.

CCI

Rescreen procedures cannot be conducted the day prior to intervention randomization if there are Day -1 procedures planned per protocol.

8.10.2 Treatment Period/Vaccination Visit

Refer to the SoA (Section 1.3) and Administrative and General Procedures (Section 8.1).

8.10.3 Participants Discontinued From Study Intervention but Continuing to be Monitored in the Study

At any point if a participant discontinues from treatment but continues to be monitored in the study, all of study procedures specified in the SoA may be completed at the discretion of the investigator and with Sponsor agreement. The subset of study procedures completed will be communicated in a PCL.

8.10.4 Poststudy

8.10.5 Critical Procedures Based on Study Objectives: Timing of Procedure

For this study, the blood sample for MK-1167 is the critical procedure.

At any postdose time point, the blood sample for MK-1167 needs to be collected as close to the exact time point as possible. All other procedures should be completed as close to the prescribed/scheduled time as possible. Study procedures can be performed before or after the prescribed/scheduled time.

The order of priority can be changed during the study with joint agreement of the investigator and the Sponsor Clinical Director.

Any nonscheduled procedures required for urgent evaluation of safety concerns take precedence over all routine scheduled procedures.

The following variance in procedure collection times will be permitted.

PK Collection as outlined in CCI

Study Intervention Administration:

08X3SB

Panel A and Panel B - Predose and Postdose Procedures:

Predose standard safety evaluations: VS and ECG within 3 hours; laboratory safety tests and physical examination within 24 hours

Panel A - Postdose standard safety evaluations: VS, ECG, laboratory safety tests, physical/neurological examination, and C-SSRS.

- Prior to 24-hours postdose may be obtained within 30 minutes of the theoretical sampling time
- Between 24-hours and 48-hours postdose may be obtained within 1 hour of the theoretical sampling time
- postdose may be obtained within 4 hours of the theoretical sampling time
- may be obtained within 30 hours.

Panel B - Postdose standard safety evaluations: VS, ECG, laboratory safety tests, physical/neurological examination, and C-SSRS.

- Prior to 24-hours postdose may be obtained within 30 minutes of the theoretical sampling time
- 24-hours postdose may be obtained within 1 hour of the theoretical sampling time
- may be obtained within 24 hours of the theoretical sampling time

Study Design/Dosing/Procedures Modifications Permitted Within Protocol 8.10.6 **Parameters**

This is a Phase 1 assessment of MK-1167 in humans, and the PK, pharmacodynamic, and safety profiles of the compound are still being elucidated. This protocol is written with some flexibility to accommodate the inherent dynamic nature of Phase 1 clinical studies. Modifications to the dose, dosing regimen, and/or clinical or laboratory procedures currently outlined may be required to achieve the scientific goals of the study objectives and/or to ensure appropriate safety monitoring of the study participants.

As such, some alterations from the currently outlined dose and/or dosing regimen may be permitted based on newly available data, but the maximum daily dose may not exceed those currently outlined in the protocol.

- Repeat of or decrease in the dose of the study intervention administered in any given period/panel
- Interchange of doses between panels
- Entire period(s) or panel(s) may be omitted
- Decrease in the duration of study intervention administration (eg, number of days)
- Adjustment of the dosing interval (eg, divided doses qd to bid, tid, or vice versa)
- Addition of PK pause
- Instructions to take study intervention with or without food or drink may also be modified based on newly available data
- Modification of the PK/pharmacodynamic sample processing and shipping details based on newly available data

The PK sampling scheme currently outlined in the protocol may be modified during the study based on newly available PK data (eg. to obtain data closer to the time of peak plasma concentrations). If indicated, these collected samples may also be assayed in an exploratory manner for metabolites and/or additional pharmacodynamic markers.

Up to additional 50 mL of blood may be drawn for safety, PK, analyses. The total blood volume withdrawn from any single participant will not exceed the maximum allowable volume during their participation in the entire study (Appendix 8).

The timing of procedures for assessment of safety procedures (eg, vital signs, ECG, safety laboratory tests, etc) may be modified during the study based on newly available data. Additional laboratory safety tests may be added to blood samples previously drawn to obtain additional safety information. These changes will not increase the number of study procedures for a given participant during their participation in the entire study.

It is understood that the current study may use some or none of the alterations described above. Any alteration made to this protocol to meet the study objectives must be detailed by the Sponsor in a letter to the Study File and forwarded to the investigator for retention. The letter may be forwarded to the IRB/IEC at the discretion of the investigator.

14-JUN-2024

